#### 10.10.4. Follow-up ( $\pm 60$ Days) at 7 and 10 Years

All implanted subjects must be evaluated in person at 84 and 120 months (7 and 10 years) after the index procedure, with a window of  $\pm 60$  days. The following assessments must be completed. The REPRISE IV eCRFs identify the specific data points to be collected.

- NYHA classification
- Current antiplatelet, anticoagulant (if applicable)
- TTE, including assessment of effective orifice area, peak and mean aortic valve gradient pressure, aortic regurgitation assessment, peak aortic velocity, and LVEF per the Echocardiography Core Laboratory procedure guidelines. All TTEs must be forwarded to the core laboratory for independent analyses.

*Note:* TTE must be done for all subjects who have a transcatheter valve implanted in the aortic position during the index procedure.

- Serious adverse event (SAE, SADE, UADE, and relevant VARC events to be adjudicated by the CEC) assessment for test device(s) and device deficiencies assessment for test device(s) with associated treatment.

*Note:* Relevant VARC events to be adjudicated by the CEC include the following: mortality, stroke, spontaneous myocardial infarction, acute kidney injury, repeat procedure for valve-related dysfunction, hospitalization for valve-related symptoms or worsening congestive heart failure (NYHA III or IV), new pacemaker, new onset atrial fibrillation or atrial flutter, prosthetic aortic valve malpositioning (valve migration, valve embolization, or ectopic valve deployment), TAV-in-TAV, prosthetic aortic valve thrombosis and endocarditis.

#### 10.10.5. Follow-up ( $\pm 60$ Days) at 6, 8 and 9 Years

All implanted subjects must be evaluated at 72, 96, and 108 months (6, 8 and 9 years) after the index procedure, with a window of  $\pm 60$  days. This evaluation may be conducted by telephone. The following assessments must be completed. The REPRISE IV eCRFs identify the specific data points to be collected.

- Current antiplatelet, anticoagulant (if applicable)

- Serious adverse event (SAE, SADE, UADE, and relevant VARC events to be adjudicated by the CEC) assessment for test device(s) and device deficiencies assessment for test device(s) with associated treatment. Please see Section **10.10.4** for a list of relevant VARC events.

### **10.11. Study Completion**

All subjects who receive a test device will be evaluated at discharge or 7 days (whichever comes first), 30 days, and then annually up to 10 years post index procedure. Visits in the first 5 years and at 7 and 10 years are office or in-person visits. Evaluations may be conducted by telephone at 6, 8 and 9 years. A subject's participation in the study will be considered complete after the 10-year visit. For subjects who do not receive a test device, participation in the study will be considered complete after the 1-year visit. Any ongoing adverse events after study completion should be managed per standard of care.

### **10.12. Source Documents**

When available, original source documents (see **Table 25.2-1** for definition) should be maintained at the investigative center. In lieu of original source documents, certified copies are required to be maintained. A certified copy is a copy (irrespective of the type of media used) of the original record that has been verified (i.e., by a dated signature [PI or as delegated by the PI] or by generation through a validated process) to have the same information, including data that describe the context, content, and structure, as the original. Source documentation includes but is not limited to those items noted in **Table 10.12-1**.

**Table 10.12-1: Source Documentation Requirements**

Requirement	Disposition
Printed, optical, or electronic document containing source data. Examples may include but are not limited to hospital records, laboratory notes, device accountability records, photographic negatives, radiographs, records kept at the investigation center, at the laboratories and at the medico-technical departments involved in the clinical investigation.	Retain at center.

*Note:* Please see **Table 25.2-1** for definitions of “source data” and “source document.”

### **10.13. Local Laboratory/Vendor Documentation**

Appropriate certifications and documentation records are required to be maintained at the investigative center for local laboratory/vendor work.

## 11. Statistical Considerations

### 11.1. Endpoints

#### 11.1.1. Primary Endpoint

The primary endpoint is the composite of all-cause mortality and all stroke at 1 year.

##### 11.1.1.1. Statistical Hypothesis for the Primary Endpoint

The statistical hypothesis is that the rate of the primary endpoint (composite of all-cause mortality and all stroke at 1 year) in the Main Cohort is less than the performance goal (PG) of 15.2% (expected rate of 11.1% plus testing margin of 4.1%).

A one-sample z-test will be used to test the one-sided hypothesis that the 1-year primary endpoint rate for LOTUS *Edge* in the Main Cohort is less than the PG:

$$H_0: P_{\text{LOTUS } Edge} \geq \text{PG}$$

$$H_1: P_{\text{LOTUS } Edge} < \text{PG}$$

where  $P_{\text{LOTUS } Edge}$  is the primary endpoint rate for the LOTUS *Edge* group and PG is the performance goal.

The primary analysis set for the primary endpoint is the intention-to-treat (ITT) analysis set (see Section 11.2.1). This endpoint will also be analyzed for the implanted analysis set.

##### 11.1.1.2. Sample Size Parameters for the Primary Endpoint

The sample size calculation for the primary endpoint is based on the following assumptions.

- Expected rate for LOTUS *Edge* = 11.1%\*
- Testing margin = 4.1% (37% relative to the expected rate)
- Performance goal (PG) = 15.2% (expected rate of 11.1% plus testing margin of 4.1%)
- Test significance level ( $\alpha$ ) = 0.025 (1-sided)
- Power = 87.5%
- Number of evaluable subjects = 675
- Expected rate of attrition = 3%
- Total enrollment (evaluable Main Cohort) = 696 subjects

\* Estimated pooled rate from the fixed effect model based on the TAVR arm data from PARTNER II S3i and SURTAVI

##### 11.1.1.3. Success Criteria – Primary Endpoint

If the  $P$  value from the one-sample z-test is  $<0.025$ , it will be concluded that the primary endpoint with the LOTUS *Edge* Valve System is less than the PG. This corresponds to the

one-sided upper 97.5% confidence bound of the observed composite rate of all-cause mortality and all stroke in the Main Cohort at 1 year being < 15.2%.

#### 11.1.1.4. Statistical Methods – Primary Endpoint

All subjects who are enrolled will be eligible for evaluation. Handling of dropouts and missing data will depend on their frequency and the nature of the outcome measure. Sensitivity analyses (e.g., tipping-point analysis) will be performed to assess the impact of subjects with inadequate follow-up (i.e., missing data) on the primary endpoint and to assess the robustness of the conclusion of the primary analysis. Statistical models that account for censored data will be employed in appropriate circumstances (e.g., for time-to-event outcomes). Suspected invalid data will be queried and corrected in the database prior to statistical analysis. Additional information may be found in the statistical analysis plan (SAP).

#### 11.1.2. **Baseline Comparability**

Baseline data will be summarized separately for subjects in the Main Cohort, Roll-In Cohort, and Bicuspid Nested Registry Cohort. Subject demographics, clinical and neurological history, risk factors, and pre-procedure characteristics will be summarized using descriptive statistics (e.g., mean, standard deviation, n, minimum, maximum) for continuous variables and frequency tables or proportions for discrete variables. Procedural characteristics will be summarized similarly.

#### 11.1.3. **Post-procedure Measurements**

Post-procedure information will be collected at regularly scheduled follow-up examinations as detailed in the clinical study schedule (see **Table 10.1-1**) and will be summarized using descriptive statistics for continuous variables (e.g., mean, standard deviation, n, minimum, maximum) and frequency tables or proportions for discrete variables. The Kaplan-Meier product-limit method will be used to estimate rates for time-to-event endpoints. Adverse event and SAE rates will be reported. No formal statistical testing will be done for the Roll-In Cohort or Bicuspid Nested Registry Cohort.

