Mean gradient (mmHg) g	11.45±5.20 (97)	12.58±5.66 (92)	12.30±6.18 (75)	11.26±5.23 (61)	12.41±6.88 (55)	14.43±6.44 (43)
Peak aortic gradient (mmHg) h	21.30±9.26 (97)	23.09±10.14 (92)	21.25±11.03 (75)	21.27±9.65 (61)	22.20±11.03 (55)	26.55±11.34 (43)
Peak aortic velocity (m/s) i	2.25±0.48 (97)	2.35±0.50 (92)	2.23±0.56 (75)	2.25±0.51 (61)	2.29±0.54 (55)	2.52±.53 (43)
Paravalvular Aortic Regurgitation						
None	78.1 (75/96)	86.4 (76/88)	87.8 (65/74)	87.5 (49/56)	74.1 (43/58)	59.1 (26/44)
Trace/trivial	5.2 (5/96)	2.3 (2/88)	2.7 (2/74)	0.0 (0/56)	10.3 (6/58)	20.5 (9/44)
Mild	15.6 (15/96)	11.4 (10/88)	9.5 (7/74)	12.5 (7/56)	13.8 (8/58)	15.9 (7/44)
Moderate	1.0 (1/96)	0.0 (0/88)	0.0 (0/74)	0.0 (0/56)	1.7 (1/58)	4.5 (2/44)
Severe	0.0 (0/96)	0.0 (0/88)	0.0 (0/74)	0.0 (0/56)	0.0 (0/58)	0.0 (0/44)

Values are presented as % (count/sample size), % (n), or mean±SD (n); for clinical events, binary rates are presented through 30 days, time-to-event (Kaplan-Meier) data are presented at 1 year and beyond.

a: Due to new conduction disturbances or arrhythmias

b: For valve-related dysfunction (surgical or interventional)

c: For valve-related symptoms or worsening congestive heart failure (NYHA class III or IV)

d: Peri-procedural

e: Including valve migration, valve embolization, ectopic valve deployment, or TAV-in-TAV

f: Baseline effective orifice area (cm^2): 0.68 ± 0.19 (11); change from baseline is significant at all time points

g: Baseline mean aortic gradient (mmHg): 53.9±20.9 (11); change from baseline is significant at all time points

h: Baseline peak aortic gradient (mmHg): 76.54±23.56 (104); change from baseline is significant at all time points

i: Baseline peak aortic velocity (m/s): 4.30±0.67 (105); change from baseline is significant at all time points

Abbreviation: AKI=acute kidney injury; EOA=effective orifice area; MI=myocardial infarction; PPM=permanent pacemaker; TAV=transcatheter aortic valve; VARC=Valve Academic Research Consortium

References: Meredith 2014, 2015, 2016; Hildick-Smith 2017; Dumonteil 2018

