#### 6.2.2. Additional Measurements

Additional measurements based on the VARC endpoints and definitions (see *Note 1* below) will be collected peri- and post-procedure, at discharge or 7 days post-procedure (whichever comes first), 30 days, and annually up to 10 years post index procedure, unless otherwise specified below.

- Safety endpoints adjudicated by an independent Clinical Events Committee (CEC; Section 21.1.1):
  - Mortality: all-cause, cardiovascular, and non-cardiovascular
  - Stroke: disabling and non-disabling

- Myocardial infarction (MI): periprocedural ( $\leq 72$  hours post index procedure) and spontaneous ( $> 72$  hours post index procedure)
- Bleeding: life-threatening (or disabling) and major (through 5 years)
- Acute kidney injury (AKI;  $\leq 7$  days post index procedure): based on the AKIN System Stage 3 (including renal replacement therapy) or Stage 2
- Major vascular complication (including annular rupture; through 5 years)
- Repeat procedure for valve-related dysfunction (surgical or interventional therapy)
- Hospitalization for valve-related symptoms or worsening CHF (NYHA class III or IV)
- New permanent pacemaker implantation resulting from new or worsened conduction disturbances (definitions in Table 25.2-1; see **Note 2** below)
- New onset of atrial fibrillation or atrial flutter
- Coronary obstruction: periprocedural ( $\leq 72$  hours post index procedure)
- Ventricular septal perforation: periprocedural ( $\leq 72$  hours post index procedure)
- Mitral apparatus damage: periprocedural ( $\leq 72$  hours post index procedure)
- Cardiac tamponade: periprocedural ( $\leq 72$  hours post index procedure)
- Prosthetic aortic valve malpositioning, including valve migration, valve embolization, or ectopic valve deployment
- Transcatheter aortic valve (TAV)-in-TAV deployment
- Prosthetic aortic valve thrombosis
- Prosthetic aortic valve endocarditis
- Device performance endpoints peri- and post-procedure:
  - Successful vascular access, delivery and deployment of the study valve and successful retrieval of the delivery system
  - Successful retrieval of the study valve if retrieval is attempted
  - Successful repositioning of the study valve if repositioning is attempted (see **Note 3** below)

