## **11.2. General Statistical Methods**

All statistical analyses will be performed using the SAS System software, version 9.2 or later (Copyright© 2000 SAS Institute Inc., SAS Campus Drive, Cary, North Carolina 27513, USA. All rights reserved).

All statistical analyses will be conducted according to applicable Standard Operating Procedures, Work Instructions, and the study-specific SAP.

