### **11.2.3. Reporting Events**

For all subjects, all events that occur from the time of enrollment will be reported. For time based clinical events, the cut-off for events for 30-day endpoints will be 30 days, for 1-year endpoints it will be 365 days, and for 2–10-year endpoints it will be 365 days times the number of years. For events at discharge or 7 days post-procedure, the cut-off for events will be the earlier of the date of discharge or 7 days post-procedure for each subject.

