### **11.3.1. Other Measurements**

Other measurements not driven by statistical hypotheses are listed in Section 6.2.2.

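### Kaplan-Meier is the only estimator named for event rates out to 10 years; with death censored, late non-fatal and cardiovascular-death rates come out modestly too high, increasingly so over follow-up

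*Combined protocol and SAP*

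**What the plan says.** Section 11.1.3 names one estimator for rates over time: "The Kaplan-Meier product-limit method will be used to estimate rates for time-to-event endpoints". The same section also plans "frequency tables or proportions for discrete variables", without saying which clinical endpoints fall under which heading.

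Section 6.2.2 collects the additional measurements "annually up to 10 years post index procedure", with bleeding and major vascular complications stopping at 5 years. The list includes cardiovascular death, stroke, myocardial infarction, hospitalization, repeat procedure, pacemaker and atrial fibrillation, each of which excludes some or all deaths. Section 11.2.3 fixes the cut-offs: "for 2–10-year endpoints it will be 365 days times the number of years".

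The only other wording on censoring is in Section 11.1.1.4: "Statistical models that account for censored data will be employed in appropriate circumstances". It gives no rule for death. Section 11.2 defers to a further document: "All statistical analyses will be conducted according to applicable Standard Operating Procedures, Work Instructions, and the study-specific SAP". That SAP is not in the text available here. Section 11.3.1 limits what is at stake: "Other measurements not driven by statistical hypotheses are listed in Section 6.2.2".

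**The concern.** When death is treated as censoring, one minus Kaplan-Meier estimates the risk that would apply if nobody died first. Readers will take a printed 5-year or 10-year rate as the share of patients who have the event, and that share is smaller. The difference grows as deaths accumulate, and this is an elderly population followed for 10 years.

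The programme has reported this way before. The notes to the REPRISE II main-cohort table (Table 4.1-4) state that "time-to-event (Kaplan-Meier) data are presented at 1 year and beyond". If REPRISE IV follows suit, its late descriptive rates will be too high. Cardiovascular and non-cardiovascular death, both listed in Section 6.2.2, would then add up to more than all deaths.

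**Working it through.** **The plan's own figure.** The plan gives no late event rate. Its one design calculation (11.1% against a performance goal of 15.2%, one-sided alpha 0.025, 675 evaluable subjects) reproduces at 87.5% power. It is not affected, because the primary composite includes death from any cause and is read at 1 year.

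**Inputs.** Printed Kaplan-Meier rates and event counts from Table 4.1-4 (REPRISE II main cohort, N=120) and Table 4.1-5 (full cohort, N=250). Both are high-risk populations.

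**Step 1: cardiovascular death, with no hazard model.** Correct cumulative incidences of cardiovascular and non-cardiovascular death must sum to all-cause mortality. At 5 years the main cohort had 50 deaths, 25 of them cardiovascular, and all-cause Kaplan-Meier was 42.6%.
- Proportional split: 42.6 × 25/50 = 21.3% each.
- Bounds: each event carries weight of at least 1/N, so each cause is at least 25/120 = 20.8%. Cardiovascular death is therefore at most 42.6 − 20.8 = 21.8%.
- Printed Kaplan-Meier: 24.0%, which is 2.7 points (1.13-fold) above the split and 2.2 points above the upper bound.
- Consistency check: cause-specific Kaplan-Meier survivals multiply to overall survival, so non-cardiovascular death would read 1 − 0.574/0.760 = 24.5%. The two would total 48.5%, against 42.6% for all deaths.

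Full cohort, 4 years: 38.7 × 42/94 = 17.3% against 19.0% printed (1.10-fold).

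**Step 2: non-fatal endpoints.** The floor is n/N. The estimate is (n/N) × w, where w = all-cause Kaplan-Meier ÷ (deaths/N) corrects for other censoring. For the main cohort in years 1–5, w = 11.0/(13/120) = 1.015, 16.9/(20/120) = 1.014, 23.1/(27/120) = 1.027, 30.8/(36/120) = 1.027 and 42.6/(50/120) = 1.022.

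| Main cohort | Yr 1 | Yr 2 | Yr 3 | Yr 4 | Yr 5 |
|---|---|---|---|---|---|
| CV death, Kaplan-Meier % | 6.7 | 10.4 | 12.3 | 16.3 | 24.0 |
| CV death, cumulative incidence % | 6.8 | 10.1 | 12.0 | 15.4 | 21.3 |
| Hospitalization, events | 6 | 9 | 13 | 18 | 20 |
| Hospitalization, Kaplan-Meier % | 5.2 | 8.0 | 12.2 | 17.5 | 19.8 |
| Hospitalization, cumulative incidence % | 5.1 | 7.6 | 11.1 | 15.4 | 17.0 |
| Hospitalization, ratio | 1.02 | 1.05 | 1.10 | 1.14 | 1.16 |
| Hospitalization, largest possible ratio | 1.04 | 1.07 | 1.13 | 1.17 | 1.19 |

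The year-1 reversal for cardiovascular death (6.8 against 6.7) is rounding; the gap there is nil. Year-5 hospitalization in full: 20/120 × 1.022 = 17.0%; 19.8/17.0 = 1.16; ceiling 19.8/16.7 = 1.19.

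Other main-cohort endpoints at 5 years:
- Life-threatening bleeding (15 events): 15.0% against 12.8%, 1.17-fold, at most 1.20.
- All stroke (14 events): 13.0% against 11.9%, 1.09-fold, at most 1.11.
- New pacemaker (42 events): 36.4% against 35.8%, 1.02-fold, at most 1.04.
- New atrial fibrillation (7 events): at most 1.03-fold.

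Full cohort, 4 years, hospitalization (41 events): w = 38.7/(94/250) = 1.029, giving 16.9% against 19.7% (1.17-fold, at most 1.20).

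The estimate assumes that other censoring affects events and deaths alike. Where events come earlier than deaths, the true value lies between the floor and the figure given. In 3,000 simulated cohorts of 120, the estimate was within 0.23 points of Aalen-Johansen in 95% of runs.

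**Step 3: illustration at intermediate risk.** Death is 6.5% or 6.7% per year, the 1-year figures in Table 4.1-1 for the two studies behind the expected rate. The event hazard e is an assumption, and all hazards are constant. With h = −ln(1 − m), where m is the yearly death risk, Kaplan-Meier = 1 − exp(−eT) and cumulative incidence = e/(e+h) × (1 − exp(−(e+h)T)).

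| Assumed e per year | 5-yr Kaplan-Meier % | 5-yr incidence % | 10-yr Kaplan-Meier % | 10-yr incidence % |
|---|---|---|---|---|
| 1% | 4.9 | 4.1 | 9.5 | 6.9–7.0 |
| 2% | 9.5 | 8.1 | 18.1 | 13.2–13.3 |
| 4% | 18.1 | 15.4–15.5 | 33.0 | 24.3–24.5 |

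This lets event-free subjects die at the whole-cohort rate, which tends to widen the gap.

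**The case against.** The premise is conditional. Section 11.1.3 does not list its time-to-event endpoints, the protocol never says that death is censored, and the SAP could settle both matters. This stands, and it limits the claim to what the public text specifies.

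Precedent is mixed. REPRISE I (Table 4.1-2) reports counts over 11 through 5 years, and REPRISE III and RESPOND keep subjects who died in the denominator at 1 year. Rates of that kind do not censor death. This also stands: the point concerns only late rates reported by Kaplan-Meier. But that is the one method Section 11.1.3 names for rates over time, and the one used in the larger long-term REPRISE II tables.

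The source tables have flaws. In Table 4.1-4, Stage 2 kidney injury goes from 2 events to 4 and back to 2, and pacemaker falls from 35.4% to 35.3% on the same count, which suggests different data cuts. Year-by-year tenths should therefore not be pressed. The rows for cardiovascular death, hospitalization, stroke and bleeding rise consistently, and the 5-year gap does not depend on the earlier columns.

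No document supports a number for this trial: REPRISE II was high risk, and the 10-year illustration uses assumed hazards with first-year mortality carried forward. Agreed; the illustration shows direction and growth only.

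Finally, the bias overstates harm, changes no decision, and Kaplan-Meier keeps comparability with REPRISE II. That is why the point is minor. Comparability can be kept by showing both. Section 11.1.4 does plan gender comparisons of additional endpoints, but names no test and makes no multiplicity adjustment.

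**Conclusion.** The concern holds, as a minor point and with medium confidence. Read in the usual way, the stated estimator overstates late non-fatal event rates and cardiovascular death. In the sponsor's high-risk data the excess is 1 to 3 points at 5 years for later-accruing endpoints (about 1.1 to 1.2-fold). It is at most about 1.04-fold at 1 year for the endpoints computed, and close to nil at 30 days. It stays small for events that occur mostly early, and would be expected to grow towards year 10 for events that keep accruing.

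This rests on death being censored, on late rates being reported by Kaplan-Meier rather than as proportions, and on the SAP not already providing otherwise. At intermediate risk the excess may be smaller at the same follow-up time. The primary endpoint and its test, the sample size and all-cause mortality are unaffected.

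**What to change.** In Section 11.1.3 and the SAP, state that non-fatal endpoints beyond 1 year will be reported as Aalen-Johansen cumulative incidence with death as the competing event, and cardiovascular death with non-cardiovascular death competing. Keep Kaplan-Meier for all-cause death and for composites that include it. It can also be shown as a supplement for comparison with REPRISE II.

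The cost is one or two sentences and slightly more analysis work; the data are already collected. Without the supplement, the late rates would be less directly comparable with the REPRISE II tables. If the SAP already specifies this, a cross-reference in Section 11.1.3 closes the point.

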#### 11.1.4. **Subgroup Analyses**

Primary and pre-specified additional endpoints will be summarized and compared for the following subgroups.

- Gender (male and female)

No adjustments for multiple comparisons will be made. Additional analyses may be performed as appropriate.

For the CT Imaging Substudy, data from the 4D CT scan at 30 days and at 1 year post LOTUS *Edge* valve implantation to assess the prevalence of reduced leaflet mobility will be summarized and the relationship, if any, to clinical events will be explored.

